8.6.1 Interim Analysis for Efficacy

At the planned interim analysis, the test statistic based on the effect size (common odds ratio) will be compared to the critical value shown below. If the test statistic exceeds the critical value, continuation of the trial will be evaluated. In order to stop the trial at the interim analysis, the significance level will need to be less than the critical p-value.

At the planned interim analysis, a two-sided test will be performed to detect either an increase or decrease in the common odds ratio. In order to preserve the over-all type I error rate at 1%, the critical value for the test statistic will be inflated above 2.575, the value that would be used if no repeated testing were used (Table 2). The actual critical values and p-values will be computed using statistical methods for group sequential testing with the O'Brien Fleming method (O'Brien and Fleming, 1979; Lee and Quan, 1993).

Table 2
Critical Values and p-Values for Planned Interim Analysis

| Interim and Final Analyses | Total Sample | Critical Value | p-value | Cumulative Type I Error |
|----------------------------|--------------|----------------|---------|-------------------------|
| Interim (1) | 400 | 3.65 | 0.0003 | 0.0003 |
| Final (2) | 1180 | 2.58 | 0.0098 | 0.0101 |

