8.6.3 Outcomes of Interim Analysis

If the p-value from the test of the null hypothesis of no treatment difference is less than 0.0003 at the interim analysis, the study could be stopped for efficacy.

No formal stopping rule for futility will be established for this study. An assessment of conditional power at the interim analysis will be provided to the DSMB for consideration with the safety summaries in the evaluation of the overall risk/benefit of the study treatment.

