During the treatment period, subjects will be administered continuous i.v. infusion of BHR-100 or matching placebo for 120 hours and the GCS and neuroworsening (defined as any one of the following: a decrease in GCS motor score ≥ 2 , development of pupillary abnormalities, any other neurological deterioration, or progression of lesion on CT scan leading to a change in subject management) will be assessed daily. Vital signs, ABGs, ICP, and CPP will be recorded periodically, and TIL, concomitant medications, and adverse events (AEs) will be monitored continuously.

During the follow-up period, subjects will be assessed at the following post-injury timepoints:

- Day 6,
- Day 15 (or ICU discharge),
- Day 30 (Month 1),
- Day 90 (Month 3),
- Day 180 (Month 6).

See the protocol schedule of events for further details of the efficacy and safety assessments conducted at each timepoint.

An independent Data Safety Monitoring Board (DSMB) will monitor data periodically during the course of the study and will update the sponsor. Reviews will occur at approximately

100-subject intervals. A DSMB charter and Data Monitoring and Analysis Plan (DMAP) have been written to provide further details.

There will be one interim analysis conducted when 200 subjects in each treatment group (400 subjects total) have reached a study endpoint (completed the study and been assessed for 6-month Glasgow Outcome Scale (GOS), died, or lost to follow up). At the interim analysis, stopping for efficacy will be assessed using statistical methods for group sequential testing with the O'Brien Fleming method.

Additionally, stopping the study for futility will be assessed by review of the conditional power at the interim analysis.

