7 INTERIM ANALYSIS

A formal interim analysis will be performed once the first 200 subjects in each treatment arm (total of 400 subjects) have reached a study endpoint (death, lost to follow up, or completed the study and assessed for the 6-month GOS). The database used for the interim analysis will only contain these 400 subjects.

At the planned interim analysis, the test statistic based on the effect size (common odds ratio) will be compared to the critical value shown below. If the test statistic exceeds the critical value, the unblinded study statisticians will discuss the continuation of the trial with the DSMB and the DSMB will inform the Sponsor. In order to stop the trial at the interim analysis, the significance level will need to be less than the critical p-value (i.e. $p < 0.0003$).

At the planned interim analysis, a 2-sided test will be performed to detect either an increase or decrease in the common odds ratio, as described in the section of this document on primary end point analysis, section 9.5.1. In order to preserve the over-all type I error rate at 1%, the critical value for the test statistic will be inflated above 2.575, the value that would be used if no repeated testing were used. The actual critical values and p-values will be computed using statistical methods for group sequential testing with the O'Brien Fleming method.

If the p-value from the test of the null hypothesis of no treatment difference is less than 0.0003 at the interim analysis, the study may be stopped for efficacy. Table 2 indicates the critical values, p-values and cumulative type I error for this study:

Table 2
Critical Values and p-Values of Interim and Final Analyses

Interim and final analyses	Total sample	Critical Value	p-value	Cumulative Type I Error
Interim (1)	400	3.65	0.0003	0.0003
Final (2)	1180	2.58	0.0098	0.0101

No formal stopping rule for futility will be established for this study. An assessment of conditional power at the interim analysis will be provided to the DSMB for consideration with the safety summaries in the evaluation of the overall risk/benefit of the study treatment.

Under the condition that the proportional odds model assumption holds, the statistical power to reject the null hypothesis of equal six-month GOS is shown below under a variety of scenarios (Table 3).

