If the p-value from the test of the null hypothesis of $\beta_1 = 0$ is less than 0.0003 (at the interim) or 0.0098 (at the final analysis), it will be concluded that BHR-100 is statistically significantly different from placebo with respect to the GOS at 6 months following injury. The odds of some degree of improvement in the GOS at 6 months will be modeled and the corresponding common odds ratio for treatment, e^{β_1} , can then be interpreted to determine the direction of the treatment difference as follows. With the placebo group being considered as the reference category, if the odds ratio (OR_{BHR-100/placebo}) is greater than 1, the odds of some improvement in the GOS at 6 months is greater in the BHR-100 treatment group compared to placebo.

In the event that the primary efficacy analysis does not show statistical significance at the study-wise 1% significance level, please refer to section 9.5.1.4 for further details on how the statistical significance of the primary efficacy analysis should be interpreted.

The POM will be fitted in SAS[®] using the PROC LOGISTIC procedure.

Goodness of fit of the model will be assessed using the Deviance and Pearson tests (add SCALE = NONE AGGREGATE to the MODEL statement of PROC LOGISTIC) to compare the fitted model with the saturated model. If these tests are not statistically significant it implies that the model fits the data adequately.

The score test for the proportional odds assumption and individual p-values associated with the tests of effects (treatment, geographic region, age, GCS motor score, pupil response, and CT classification) will be summarized for the POM of GOS at 6 months post injury.

The odds ratios and associated 95% CIs for the levels of the effects relative to a reference category will be presented for all factors and covariates included in the POM of GOS at 6 months post injury.

In addition to the results of the hypothesis tests from the statistical modeling, the number of non-missing observations, absolute and relative frequency (n and percentages), will be provided by treatment group for the GOS categories at 6 months post injury.

The analyses above will be repeated for the straight observed case analysis (no imputation of 6-month GOS or covariates) in the mITT population, the straight observed case analysis in the PP population (no imputation of 6-month GOS or covariates), and the analysis of imputed missing values in the mITT population for US subjects only.

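### Table 2's boundary is not the O'Brien-Fleming boundary for a look at 400 of 1180, and Table 3's interim powers do not follow from it; the 1% error rate is still held

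*SAP*

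**What the plan says.** Both documents plan one efficacy look, at 400 of 1180 subjects, with a two-sided test and an overall type I error of 1%.

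- **Method.** SAP section 3 says that "stopping for efficacy will be assessed using statistical methods for group sequential testing with the O'Brien Fleming method". SAP section 7 and Protocol 8.6.1 add: "The actual critical values and p-values will be computed using statistical methods for group sequential testing with the O'Brien Fleming method".
- **Boundary.** SAP section 7 states: "Table 2 indicates the critical values, p-values and cumulative type I error for this study". The same table is in Protocol 8.6.1. Its rows read "Interim (1) | 400 | 3.65 | 0.0003 | 0.0003" and "Final (2) | 1180 | 2.58 | 0.0098 | 0.0101" (look, total sample, critical value, p-value, cumulative type I error).
- **Decision rule.** The trial may stop for efficacy if the p-value "is less than 0.0003 at the interim analysis, the study may be stopped for efficacy"; Protocol 8.6.3 has the same threshold. The primary test in SAP 9.5.1.1 declares a difference if the p-value "is less than 0.0003 (at the interim) or 0.0098 (at the final analysis"). The two thresholds recur in Protocol 8.3 and 8.3.1 and in SAP 9.5.1.2.
- **Interim power.** Table 3 (SAP section 7, Protocol 8.6.2) gives 1.54%, 10.93% and 88.49% at 400 completed subjects for common odds ratios of 1.27, 1.5 and 2.33. The final powers are 39.36%, 90.66% and 99.99%.

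**The concern.** O'Brien-Fleming boundaries are strict at early looks. At about a third of the information and an overall 1%, an interim critical value of 3.65 is too low for that method. If the label is wrong, a reader cannot recover the boundary from the description, and someone who enters the named method with a look at 400 of 1180 into group sequential software will not get Table 2. That matters for reproducibility, because Protocol 8.3 and SAP 9.5.1.4 require the adjusted final p-value to use the pre-specified boundaries.

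Table 3 should follow from Table 2. If it does not, the plan misstates how likely the trial is to cross at the interim. The first thing to establish is whether the 1% error rate is at risk.

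**Working it through.** **Inputs.** Overall two-sided alpha 0.01, looks at 400 and 1180 (SAP section 7). Placebo distribution 31/21/19/29% (SAP 3.1, Protocol 8.1); the footnote to the protocol's Table 3 has 30/21/19/30%, run as a variant. Odds ratios 1.27, 1.5 and 2.33 (Table 3). Assumption: information is proportional to subjects, so t = 400/1180 = 0.339 and the correlation between the two statistics is √0.339 = 0.582.

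**1. Where 3.65 / 2.58 comes from.** Classical O'Brien-Fleming with two looks uses c1 = C/√t and c2 = C, with C solved so that 1 − P(|Z1|<c1, |Z2|<c2) = 0.01.

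- t = 0.5: C = 2.580 and c1 = 2.580/0.7071 = 3.648. This is Table 2's pair.
- t = 0.339: C = 2.576 and c1 = 2.576/0.582 = 4.424 (p about 0.00001).
- O'Brien-Fleming-type spending at t = 0.339: about 4.42 with the two-sided 0.01 spent as a whole, and 4.68 with 0.005 spent on each side.

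**2. Error of the rule in use.** Joint two-sided error at t = 0.339:

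| Interim / final | Joint error |
|---|---|
| p<0.0003 / p<0.0098 (z 3.615 / 2.583) | 0.009998 |
| 3.65 / 2.58 as printed | 0.01005 |
| 3.62 / 2.58 | 0.01007 |

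The printed critical values and p-values agree only to rounding: 3.65 is p = 0.00026, and 2.58 is p = 0.0099.

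**3. Check of the power formula on the plan's own figures.** For 1:1 allocation, drift = ln(OR)·√[(N/12)(1 − Σp̄³)], where p̄ are the category proportions averaged over arms, and power = Φ(drift − c). At OR 1.5, Σp̄³ = 0.0766.

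- Sample size at alpha 0.01 and 90% power: 12 × (2.576 + 1.282)² / (0.1644 × 0.9234) = 1176. At alpha 0.0098 it is 1180, the planned number.
- Final powers at p<0.0098: 38.2%, 90.0% and >99.99%, against 39.36%, 90.66% and 99.99% printed.

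The formula therefore fits the final column to within about 1.2 points.

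**4. Interim powers at N = 400.** For OR 1.5, drift = 0.4055 × √(33.33 × 0.9234) = 2.250. At p<0.0003, power = Φ(2.250 − 3.615) = 8.6%.

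| Threshold | OR 1.27 | OR 1.5 | OR 2.33 |
|---|---|---|---|
| Table 3 as printed | 1.54% | 10.93% | 88.49% |
| p<0.0003 | 1.11% | 8.60% | 84.98% |
| 3.65 | 1.01% | 8.07% | 84.15% |
| 4.424 | 0.10% | 1.48% | 58.97% |
| p<0.0005 (3.481) | 1.57% | 10.91% | 87.90% |

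The 30/21/19/30 variant moves the p<0.0003 row by at most about 0.2 points. Using placebo-only proportions raises OR 2.33 at p<0.0003 to 86.3%. Simulation of the unadjusted score test (400,000 trials, 31/21/19/29) gives 1.06%, 8.31% and 83.8% at p<0.0003; simulation of the Wald test from the fitted proportional odds model (100,000 trials) gives 1.05%, 8.25% and 83.8%. A half-way look does not explain the column either: 590 subjects at 3.65 gives about 2.1%, 18% and 98%.

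**The case against.** **Nobody could apply the wrong threshold.** This stands. p<0.0003 and p<0.0098 are written into the decision rules in both documents. The future tense of the method sentence could suggest that the values would be recalculated at the look, but the fixed thresholds and the sentence introducing Table 2 speak against that.

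**4.42 is not the only O'Brien-Fleming value at this look, and the source of the printed pair cannot be established.** This also stands. Protocol 8.6.1 cites a further approximation method, and SAP section 3 refers to a DSMB charter and a monitoring plan that are not part of these documents. The mismatch survives, because each version tried gives at least 4.42, well above 3.65.

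**The power check is unadjusted, while the planned test is covariate-adjusted, and Table 3 states no method.** True. What the check supports is that the interim column does not reproduce from the printed boundary, while the same formula fits the final column.

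Three stronger readings are tempting and are not supported:

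- A reader might infer that alpha is inflated, the more so because Table 2 prints a cumulative error of 0.0101. The p-value rule has a joint error of 0.0100. The printed 0.0101 fits the rounded critical values (0.01005), and it also equals the sum 0.0003 + 0.0098.
- A reader might infer that the trial really used an interim threshold of p<0.0005, because that value fits Table 3's interim column. It is solved backwards from three printed powers and appears in neither document, so it is conjecture.
- A reader might infer that the Table 3 figures steer the trial. There is no formal futility rule, and the DSMB is to receive conditional power calculated at the interim.

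**Conclusion.** The point holds as a minor correction of stated method and figures.

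The boundary is described as O'Brien-Fleming for a look at 400 of 1180, but it is that method's half-way pair. Under the printed rule the chance of crossing at OR 1.5 is about 8-9%; at 4.42 it would be about 1.5%. In terms of the observed (unadjusted) odds ratio, crossing takes about 1.92 at p<0.0003 and about 2.23 at 4.42. The printed rule is thus easier to cross than the named method implies, yet it holds the overall 1%.

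At p<0.0003, allowing for the formula variants and the simulations, Table 3 overstates the interim powers by 0.4-0.5 points at OR 1.27, 2.2-2.7 at OR 1.5 and 2.2-4.7 at OR 2.33.

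Sample size and final power are unaffected: overall power at OR 1.5 is about 90% under either boundary. The effect on the adjusted final p-value was not calculated. The result rests on information proportional to subjects and, for the powers, on unadjusted calculations under proportional odds.

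**What to change.** - Keep p<0.0003 and p<0.0098. In SAP sections 3 and 7 and Protocol 8.6.1, describe them as a fixed pre-specified boundary that holds 1% overall, and remove the statement that they are computed by O'Brien-Fleming at this look.
- Recompute Table 3's interim column from p<0.0003 at 400 subjects and state the method. Expect about 1%, 8-9% and 84-86%; the exact figures should come from the sponsor's own software.
- Tidying Table 2 is optional. If it is done, change both critical values together to match the p-values (3.615 and 2.583, cumulative error 0.0100). Changing only the interim value would leave 3.62 with 2.58, which again gives 0.0101.

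The cost is wording and a few table entries in two documents. No threshold, sample size or procedure changes. SAP 1.1 shows that the trial is under a Special Protocol Assessment, so the sponsor should check whether rewording the named method needs the agency's agreement; the documents do not say.

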8 DATA REVIEW

8.1 Data Handling and Transfer

For this study PRA International provides full Data Management services, including the development of the Data Management Plan (DMP) which outlines all Data Management activities to be undertaken. The DMP is a living document that evolves over the course of a trial and consists of the following documents:

- Data Management Process Summary,
- Annotated CRF,
- Data Management Quality Control Plan,
- Critical Variable List,
- Data Edit Specifications,
- Dictionary Coding Conventions,
- SAE/AE Reconciliation Plan,
- Electronic Clinical Data Handling Instructions, and
- Database Conversion Specifications.

For this study, PRA International defines and maintains the study database. The database will be provided to the PRA International Analysis and Reporting group in SAS dataset format.

Assessments will be conducted at the central bioanalytical laboratory for blood levels of progesterone.

8.2 Data Screening

Beyond the data screening built into the PRA DMP, programming of analysis datasets, tables, figures, and listings will be ongoing during the data management of the study. During this process potential data issues will be communicated to Data Management. Before the data are considered clean (as defined by PRA Data Management processes), blinded tables, figures, and listings will be run (using a dummy randomization) and distributed to the study team for review. Any data values requiring investigation or correction will be identified at that point, and protocol deviations will be reviewed and documented. Once all data issues have been resolved, the database will be locked, treatment codes unblinded, and the final run of outputs will take place.

Furthermore, during the conduct of the study, an independent DSMB will meet to conduct safety reviews of the data, at approximately 100-subject intervals. The duties, operational procedures, and frequency of meetings/teleconferences are described in the DSMB Charter. At each meeting, the DSMB can recommend early trial termination or study modification in response to safety concerns.

The DSMB can request additional, unplanned, unblinded analysis of primary outcome data in case of major safety issues from the safety analysis. Therefore, the DSMB will be able to monitor the study in its completeness by analyzing the overall risk/benefit of the trial results as necessitated by safety concerns that may arise.

9 STATISTICAL METHODS

All analyses and reporting of study results will be conducted using SAS V9.1.3 In addition EAST will be used to adjust for the interim analysis.

All variables will be presented using appropriate descriptive statistics according to the variable nature:

- Continuous variables: number of non-missing observations, mean, standard deviation , minimum, first quartile (Q1), median, third quartile (Q3), maximum,
- Categorical variables: number of non-missing observations, absolute and relative frequency (n and percentages (%)),
- Time-to-event variables: number of non-missing observations, number and percentage of censored observations, first quartile, median (and 95% CI), third quartile, and Kaplan-Meier survival curves.

The behavior over time of continuous variables will be analyzed by presenting descriptive statistics for each time point and the difference compared to baseline (actual values and change from baseline). The behavior over time of categorical data will be analyzed by presenting the descriptive statistics for each time point and the shift compared to baseline.

The decimal places for summary statistics and percentages will be as follows:

- Precision of data + 2 decimal places (dp) for standard deviations,
- Precision of data + 1 dp for means, medians and quartiles,
- Same precision as data for minimum and maximum,
- 1 dp for percentages except when the percentage is 100% in which case no dp would be presented, and

The primary and confirmatory efficacy analyses will be 2-sided and conducted at a 1% significance level. All secondary efficacy tests will be 2-sided and conducted at a 5% significance level.

The randomization will be stratified by region. This variable will be included as a covariate in the primary and secondary GOS efficacy analyses.

Secondary efficacy analyses will be conducted in ranked order as listed in Section 9.5.2 with the understanding that no confirmatory claims can be based on variables that have a rank lower than or equal to that variable whose null hypothesis was the first that could not be rejected at the $p<0.05$ significance level.

All exploratory analyses will be considered supportive in nature, and therefore no adjustment will be made for multiple testing of exploratory variables.

All data will be included in subject data listings for all subjects in the mITT population.

9.1 Subject Disposition

An enrollment summary will be presented overall and by site, showing the first date of consent, the date of the last subject randomized, duration (in days) (calculated as end date – start date +1), and number of subjects randomized and completed endpoint.

The number and percentage of subjects randomized in total, by site, by country and by region will be summarized for each treatment group and overall for the mITT population.

The number and percentage of subjects in each study population (mITT (randomized and treated with i.v. study drug), randomized but not treated, PP, Safety, Study Completers, Endpoint Completers (includes deaths prior to Month 6), and Early Terminations) and the reasons for early termination will be summarized by treatment group and overall for mITT subjects.

Subjects remaining in the study by time will also be summarized.

These details will also be listed.

9.2 Protocol Deviations and Violations

Subjects with protocol violations that result in exclusion from the PP population will be listed.

9.3 Treatments

9.3.1 Extent of Study Drug Exposure

The number of subjects in each of the following categories will be summarized for each treatment group and overall for the safety population:

- Who initiated study drug within 8 hours of injury,
- Who were treated for at least 96 hours,
- Who prematurely discontinued study drug (with the corresponding reason for discontinuation).

Duration of study drug exposure and total dose will also be summarized for the safety population. The duration of study drug exposure (in hours) will be summarized as both a continuous and categorical variable by treatment group and overall. Total dose (in mg/kg) will also be summarized as a continuous variable. Total dose received in milligrams will be adjusted by a subject's weight entered into IWRs at the time of randomization.

Continuous and categorical summaries of time since injury to study drug initiation will be presented.

Counts and percentages of subjects with any infusion rate modifications or interruptions, and the reasons for infusion rate modifications and interruptions, will be summarized by treatment group and overall for the safety population.

The percentage compliance with study medication will be summarized by treatment group and overall for the safety population as a continuous variable. See Section 5 for further details.

